8.1.3 Storage, Stability and Handling

The daratumumab vials should be stored in the original carton in a refrigerator at 2°C to 8°C and must not be utilized after the expiry date printed on the label. The product must be protected from light and must not be frozen. Since daratumumab does not contain preservatives, any unused portion remaining in the vial must be discarded. Daratumumab will be diluted in a sterile, pyrogen-free physiological saline solution (0.9% NaCl) prior to IV administration.

8.1.4 Compatibility, Preparation and Administration

Daratumumab drug product is a colorless to yellow liquid concentrate. It is presented at a target concentration of 20 mg/mL in a 6R or 25R vial with a nominal fill volume of 20 mL, respectively. It is administered by the intravenous (IV) route after dilution in a sterile, pyrogen-free physiological saline solution (0.9% NaCl) provided by the investigation site.

Infusion bags/containers must be made of polyvinylchloride (PVC), polypropylene (PP),

polyethylene (PE), or polyolefin blend (PP+PE).

Following dilution, the infusion bag/container may be stored for up to 24 hours in a refrigerator at 2 °C to 8 °C (36 °F to 46 °F), protected from light. Infusion should be completed within 15 hours. Do not store any unused portion of the infusion solution for reuse. Any unused product or waste material should be disposed of in accordance with local requirements.

Administer the diluted solution by intravenous infusion using an infusion set fitted with a flow regulator and with an in-line, sterile, non-pyrogenic, low protein-binding polyethersulfone (PES) filter (pore size 0.22 or 0.2 micrometer). Polyurethane (PI), polybutadiene (PBD), PVC, PP, or PE administration sets must be used.

8.1.5 Availability and Ordering

Daratumumab will be provided free of charge by Janssen Scientific Affairs, LLC as 400mg/20ml vials. Biologics, Inc. will provide drug distribution services for the study. In the event that 400mg/20mL vials are not available, Janssen Scientific Affairs, LLC will provide an equivalent formulation of daratumumab in 100mg vials as a substitute.

Biologics, Inc. contact details for drug ordering:

[contact]

Email: [contact]

Throughout the course of the study, a Biologics, Inc. clinical hotline support, staffed with clinical pharmacists, is made available 24/7/365 in the event an investigator or site coordinator has a question. **Hotline [contact]

8.1.6 Accountability

The investigator, or a responsible party designated by the investigator, should maintain a careful record of the inventory and disposition of the agent using the NCI Drug Accountability Record Form (DARF) or another comparable drug accountability form. (See the NCI Investigator's Handbook for Procedures for Drug Accountability and Storage.)

8.1.7 Destruction and Return

The Drug Accountability Log will contain the date and amount of study drugs received and dispensed. All used and partially used study drug will be destroyed by the site, in accordance with the site's standard operating procedures (SOPs). All expired drug and any unused drug remaining once all patients are off study treatment will be destroyed on site in accordance with the site's standard operating procedures (SOPs).

9. BIOMARKER, CORRELATIVE, AND SPECIAL STUDIES

9.1 Biomarker Studies

9.1.1 Laboratory Correlative Studies

Bone marrow aspirate (approximately 30 cc in 2 heparinized syringes & 1 purple top or 3 purple tops for outside sites) will be collected at baseline, prior to administration of cycle 7, and within 4 weeks following completion of therapy. At each time point, the samples will be genotyped for MYD88 and CXCR4 by the Bing Center for WM laboratory. The samples will be used until depletion. All samples from sites other than DFCI will be shipped ambiently priority overnight Monday-Thursday by a qualified carrier to:

[name]
Administrative Director
Dana-Farber Cancer Institute, Harvard Medical School Bing Center for Waldenstrom's
Macroglobulinemia
[name]
[name]
Ph: [contact]
Fx: [contact]
[contact]

10. STUDY CALENDAR

	Screening* ≤ 30 days from study entry	Treatment Phase							Off Treatment Assessment Within 4 weeks of completion or removal from study ± 2 weeks	Follow-Up Phase Post Treatment; Every 12 ± 2 weeks for 24 months or until next therapy
		Induction Cycles 1 and 2 (+/- 3 days)				Consolidation (Beginning 2 weeks +/- 3 days after C2 completion) Cycles 3 to 6		Maintenance (Beginning 4 weeks +/- 7 days after C6 D15) Cycles 7 to 18		
		Day 1	Day 8 (+/- 3 days)	Day 15 (+/- 3 days)	Day 22 (+/- 3 days)	Day 1 (+/- 3 days)	Day 15 (+/- 3 days)	Day 1 (+/- 3 days)		
Physical exam ¹ , weight, height	X	X				X		X	X	X
Medical History	X									
ECOG performance status (see Appendix A)	X	X				X		X	X	X
CT of the chest & abdomen / pelvis ²	X							X ²	X ²	X (if applicable)
Bone marrow biopsy and aspiration ³	X							X ³	X ³	X (if applicable)
Serum immuno- electrophoresis & Response assessment	X	X				X		X	X	X
Serum IgM	X	X	X	X	X	X	X	X	X	X
Serum IgA, IgG	X	X				X		X	X	X
Complete Blood Count plus differential ¹	X	X	X	X	X	X	X	X	X	X
Coagulation profile: PT, PTT, PT-INR	X									
Chemistry including: Electrolytes, Renal (BUN, Creatinine) and Hepatic function testing [ALT, AST, Alk phos, total Bilirubin], albumin, total protein	X	X	X	X	X	X	X	X	X	X
Vital signs (Temp, HR, RR, BP)**	X	X	X	X	X	X	X	X		
Beta-2 microglobulin, Von Willebrand screening	X									
Pregnancy Test ⁴	X									
HBsAg, HBsAb, HBcAB	X	X ⁶				X ⁶		X ⁶		
HCV Ab	X									
Indirect antiglobulin testing	X									
Daratumumab administration		X	X	X	X	X	X	X		
Adverse event monitoring ⁵		X				X		X	X	X

* Physical exam, laboratory tests, vital signs, and weight do not need to be repeated if Cycle 1, Day 1 is within 14 days of Screening. Cycle 1, Day 1 labs, if drawn, do not need to re-confirm eligibility prior to administering first dose.

**Vital signs (Blood pressure, heart rate, respiratory rate, temperature) should be taken prior to infusion, and every 60 minutes during the infusion period (± 10 minutes), and 30 minutes (± 5

minutes) after the completion of the infusion.

¹More frequent visits may be required at the discretion of the treating physician.

²**If CT scans of the chest, abdomen and pelvis have been collected and done within 90 days of Cycle 1 Day 1 they will not be required at the screening visit. If the participant has known extramedullary disease outside the chest, abdomen, or pelvis, imaging should be performed with investigator-preferred modality.** Scans will be repeated just before Cycle 7 and at End of Treatment for participants with extramedullary disease at baseline defined as adenopathy >1.5 cm in any axis, and splenomegaly >15 cm in the craniocaudal axis. If participant has disease only outside chest, abdomen, and pelvis, only the affected area will need to be re-imaged with the same modality as at screening. Scans will also be repeated to confirm a complete response, if the participant has no detectable monoclonal protein and had extramedullary disease at baseline and at the discretion of the investigator.

³ **If bone marrow aspirate and biopsy had been collected within 90 days of Cycle 1 Day 1 they will not be required at the screening visit.** Bone marrow biopsy and aspiration will be performed just before cycle 7 and at the end of treatment. Bone marrow aspiration and biopsy may also be done at the investigator's discretion, and at any time to confirm a complete response, if the participant has no detectable monoclonal protein.

⁴For women of childbearing potential only: Serum pregnancy test is required at screening.

⁵Please refer to Section 6 for Dose Delays.

⁶Participants who have serologic evidence of HBV exposure at screening but are HBsAg negative and do not have active HBV infection are allowed to enroll on study. Participants with resolved infection (ie, subjects who are HBsAg negative but positive for antibodies to hepatitis B core antigen [anti-HBc] and/or antibodies to hepatitis B surface antigen [anti-HBs]) must be screened using real-time polymerase chain reaction (PCR) measurement of hepatitis B virus (HBV) DNA levels. Those who are PCR positive will be excluded. Participants who have unclear interpretation (HBsAg negative and anti-HBc positive and anti-HBs negative) must also be screened using real-time PCR and those who are PCR positive will be excluded. Retesting of HBV DNA only should be done every three months while on therapy for any participants with evidence of prior HBV exposure at screening.

11. MEASUREMENT OF EFFECT

11.1 Definitions

Evaluable for toxicity: All participants who receive at least one dose of study treatment will be evaluable for toxicity from the time of their first treatment.

Evaluable for objective response: Only those participants who have measurable disease present at baseline, have received at least one cycle of therapy, and have had their disease re-evaluated will be considered evaluable for response. Response will be assessed on Day 1 of each cycle starting with Cycle 2 unless the participant has undergone plasmapheresis within the previous 4 weeks. Participants discontinuing BTK inhibitors might not be evaluable for response due to IgM rebound until Cycle 4 Day 1 (Gustine JN, et al. Ibrutinib discontinuation in Waldenstrom macroglobulinemia. *Am J Hematol* 2018; 93:511-517). These participants will have their response classified according to the definitions stated below. (Note: Participants who exhibit objective disease progression or die prior to the end of cycle 1 will also be considered evaluable.)

11.2 Response Criteria

Complete Response (CR): A complete response (CR) is defined as having resolution of WM related symptoms, normalization of serum IgM levels with complete disappearance of IgM paraprotein by immunofixation, and resolution of any adenopathy or splenomegaly. A complete response requires reconfirmation demonstrating normal serum IgM levels, and absence of IgM paraprotein by immunofixation by a measurement repeated at least 2 weeks later.

Very Good Partial Response (VGPR): is defined as $\geq 90\%$ reduction in serum IgM levels, or normalization of serum IgM levels.

Partial Response (PR): Partial response (PR) is defined as achieving a $\geq 50\%$ reduction in serum IgM levels.

Minor Response (MR): A minor response (MR) is defined 25-49% reduction in serum IgM levels.

Progressive Disease (PD): Progressive disease (PD) is defined as occurring when a greater than 25% increase in serum IgM level occurs with an absolute increase of at least 500 mg/dL from the lowest attained response value, or progression of clinically significant disease related symptom(s). Reconfirmation of the initial IgM increase is required when IgM is the sole criterion for progressive disease confirmation. Death from any cause or initiation of a new anti-neoplastic therapy will also be considered a progression event. An increase of 1 cm in any axis for adenopathy, or 2 cm in the craniocaudal axis of the spleen will be considered evidence of progression of extramedullary disease. Development of Bing Neel syndrome, or other extramedullary disease manifestations, as well as disease transformation will be considered as progressive events.

Stable Disease (SD): Stable disease is defined as having $< 25\%$ change in serum IgM levels, in

the absence of new or increasing adenopathy or splenomegaly and/or other progressive signs or symptoms of WM.

Overall Response Rate (ORR): Includes patients who achieved MR, PR, VGPR and CR. The best overall response rate will be at any point on therapy.

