3. PARTICIPANT SELECTION

3.1 Eligibility Criteria

Participants must meet the following criteria on screening examination to be eligible to participate in the study:

- 3.1.1 Clinicopathological diagnosis of Waldenström Macroglobulinemia (Owen et al. 2003), and meeting criteria for treatment using consensus panel criteria from the Second International Workshop on Waldenström macroglobulinemia (Kyle et al. 2003)
- 3.1.2 Bone marrow at screening positive for CD38 expression by flow cytometry and/or immunohistochemistry
- 3.1.3 At least one previous treatment for WM with either documented disease progression or no response (stable disease) to the most recent treatment regimen
- 3.1.4 Measurable disease, defined as presence of serum immunoglobulin M (IgM) with a minimum IgM level of >2 times the upper limit of normal of each institution is required
- 3.1.5 Participants with symptomatic hyperviscosity or serum IgM >5,000 mg/dL to undergo plasmapheresis prior to treatment initiation
- 3.1.6 Age \geq 18 years
- 3.1.7 ECOG performance status \leq 2 (see Appendix A)
- 3.1.8 Participants must have preserved organ and marrow function as defined below:
 - Absolute neutrophil count \geq 1,000/mcL
 - Platelets \geq 50,000/mcL
 - Hemoglobin \geq 8 g/dL
 - Total bilirubin \leq 1.5 mg/dL or $<$ 2 mg/dL if attributable to hepatic infiltration by neoplastic disease
 - AST/ALT \leq 2.5 \times institutional upper limit of normal
 - EGFR \geq 30 ml/min
- 3.1.9 Not on any active therapy for other malignancies with the exception of topical therapies for basal cell or squamous cell cancers of the skin. Participants progressing on ibrutinib therapy (or other BTK inhibitor) may continue on therapy through screening, stopping at least 1 day prior to Cycle 1 Day 1.
- 3.1.10 Females of childbearing potential (FCBP) must agree to use two reliable forms of contraception simultaneously or have or will have complete abstinence from heterosexual intercourse during the following time periods related to this study: 1) while participating in the study; and 2) for at least 90 days after discontinuation from the study. FCBP must be referred to a qualified provider of contraceptive methods if needed. FCBP must have a negative serum pregnancy test at screening.
- 3.1.11 Men must agree to use a latex condom during sexual contact with a FCBP even if they have had a successful vasectomy.
- 3.1.12 Able to adhere to the study visit schedule and other protocol requirements.

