Daratumumab treatment should be resumed when the toxicity has resolved to \leq Grade 2. If the daratumumab administration does not commence within the pre-specified window (+/- 3 days and at least 5 days between doses) of the scheduled administration date, then the dose will be considered a missed dose. Administration may resume at the next planned dosing date. A missed dose will not be made up. If participants require a dose delay for plasmapheresis then the dose can be given up to 1 week later. This would not be considered a missed dose. If more than 2 consecutive planned doses of daratumumab are missed due to AEs, treatment continuation should be discussed with the overall PI before resumption of therapy.

Potential for IgM flare

Abrupt increases in serum IgM levels following administration of anti-CD20 monoclonal antibodies and intravenous immunoglobulin are well recognized in WM patients (Treon et al, Ann Oncol 2004; Ghobrial et al, Cancer 2004; Yang et al, ASH 2010; Furman et al, ASH 2011). Such abrupt increases can prompt symptomatic hyperviscosity in patients with high serum IgM levels, i.e. >5,000 mg/dL and can contribute to worsening of IgM related morbidity such as cryoglobulinemia, cold agglutininemia, and demyelinating neuropathy. Plasmapheresis is therefore used to treat symptomatic IgM flares, as well as prophylax in patients with high serum IgM levels. Following plasmapheresis, serum IgM levels will return to steady state in 5 weeks. As such, WM patients who undergo plasmapheresis will be non-evaluable for response purposes within 4 weeks of last plasmapheresis. It is recommended that patients with symptomatic hyperviscosity or a pre-treatment serum IgM level >5,000 mg/dL undergo plasmapheresis before treatment with daratumumab. Treatment with daratumumab may be delayed for up to one week if plasmapheresis

is warranted. Close serial monitoring of serum IgM levels (at least weekly) is recommended for all participants during cycles 1 and 2. After cycle 2, monitoring would be per protocol on Days 1 & 15 of Cycles 3-6, and Day 1 of Cycles 7-18 unless directed otherwise by treating physician.

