13.6 Analysis of Secondary Endpoints

Secondary analyses will be performed in the FAS. Time to progression (TTP) will be estimated using Kaplan Meier methodology with median time plus 25th and 75th percentile along with 95% confidence intervals, as appropriate.

Minor, partial, very good partial, and complete response rates will be estimated in the FAS population by calculating the proportion of patients having those responses and calculating the 95% confidence intervals around these point estimates.

All participants who receive at least one dose of daratumumab during the study will be included in the safety analysis.

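### Can IgM that merely re-accumulates after pre-treatment plasmapheresis be scored as progression at Cycle 2 Day 1?

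*Combined protocol and SAP*

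**What the plan says.** Section 11.2 gives this IgM test for progression: "greater than 25% increase in serum IgM level occurs with an absolute increase of at least 500 mg/dL from the lowest attained response value". A rise in IgM alone must be reconfirmed, with no interval stated. Minor response begins at a 25% IgM reduction, and Section 13.5 uses the same threshold for the primary endpoint. Neither section names the value from which the reduction is measured.

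Plasmapheresis before treatment is built into the design. Section 3.1.5 reads: "Participants with symptomatic hyperviscosity or serum IgM >5,000 mg/dL to undergo plasmapheresis prior to treatment initiation". Section 6 has IgM back at steady state after 5 weeks, allows a treatment delay of up to one week for plasmapheresis, and states that "WM patients who undergo plasmapheresis will be non-evaluable for response purposes within 4 weeks of last plasmapheresis".

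Section 11.1 sets the timing: "Response will be assessed on Day 1 of each cycle starting with Cycle 2". The exception attached to that schedule reads "unless the participant has undergone plasmapheresis within the previous 4 weeks". The section adds that "Participants discontinuing BTK inhibitors might not be evaluable for response due to IgM rebound until Cycle 4 Day 1". The Section 10 calendar has one combined row, "electrophoresis & Response assessment", marked at Screening and in the Day 1 column that Cycles 1 and 2 share. Under Sections 1.1 and 10, Cycle 1 Day 1 laboratory tests can be skipped if screening was within 14 days.

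Progression feeds PFS (Section 11.3) and the secondary analysis in Section 13.6: "Time to progression (TTP) will be estimated using Kaplan Meier methodology".

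**The concern.** The 4-week bar is attached to the date of the assessment. It says nothing about the value with which that assessment is compared. With 28-day cycles, a participant who has plasmapheresis the day before Cycle 1 Day 1 reaches Cycle 2 Day 1 on day 29, just outside the bar. No earlier on-treatment response exists then, so a rise has to be measured from something drawn before or at the first dose. If that is the lowered Cycle 1 Day 1 value, ordinary re-accumulation could pass both progression thresholds. Reconfirmation would not remove the error, because the recovered level persists.

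The direct effect would be on PFS and time to progression. ORR would be touched in two ways: a lowered baseline makes a 25% reduction harder to reach, and progression takes a participant off therapy (Section 5.5) before a later response can appear. As an illustration only, if one of the 30 participants could never count as a responder, the exact power of the rule of at least 18 responses at a true ORR of 70% would fall from 0.916 to 0.871.

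**Working it through.** **Inputs from the documents.** Cycle length 28 days (Section 5.1). Return to steady state in 5 weeks, 4-week non-evaluable window and delay of up to one week (Section 6). Progression above 25% and at least 500 mg/dL; minor response at 25% (Section 11.2). Plasmapheresis trigger above 5,000 mg/dL (Section 3.1.5). No sample-size figure is at issue.

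**Assumptions, not in the documents.** Plasmapheresis removes a share r = 25-50% of IgM; disease is unchanged; recovery is linear, f(d) = d/35, or exponential with 95% regained at day 35, f(d) = 1 - exp(-d ln20/35).

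**Step 1: lowered Cycle 1 Day 1 value as reference.** With plasmapheresis k days before Cycle 1 Day 1,

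rise = [1 - r(1 - f(k+28))] / [1 - r(1 - f(k))] - 1.

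For k = 1, r = 0.25, linear: f(1) = 0.0286 and f(29) = 0.8286, so the rise is 0.9571/0.7571 - 1 = 26.4%.

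| k | recovery | r = 25% | r = 30% | r = 50% | r at which the rise reaches 25% |
|---|---|---|---|---|---|
| 1 | linear | 26.4% | 33.9% | 77.8% | 24.0% |
| 1 | exponential | 27.1% | 34.5% | 77.1% | 23.5% |
| 7 | linear | 25.0% | 31.6% | 66.7% | 25.0% |
| 7 | exponential | 14.5% | 17.9% | 34.4% | 39.3% |

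At a steady state of 5,000 mg/dL the absolute rise is 624-2,086 mg/dL, so the 500 mg/dL floor gives no protection. If the full trough right after plasmapheresis were the reference, with day 29 as the assessment, the removal needed would be 20.4-23.2% (the lower figure assumes 99% recovery at day 35).

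Against this baseline, a scored 25% reduction needs a true reduction of 1 - 0.75[1 - r(1 - f(k))]: 42-61% for k = 1 and 35-55% for k = 7.

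**Step 2: how much drug effect removes the false progression.** Solve (1 + rise)(1 - d) = 1.25 for k = 1:
- r = 25%: d = 1 - 1.25/1.264 = 1.1% (linear), 1 - 1.25/1.271 = 1.7% (exponential).
- r = 30%: d = 6.6% to 7.1%.
- r = 50%: d = 29.4% to 29.7%.

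Only heavy removal survives a modest fall in IgM after four weekly infusions.

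**Step 3: pre-plasmapheresis screening value as baseline.** The distortion at day 28 is a false reduction of r(1 - f(28)):
- linear: 0.25 × 0.20 = 5.0%; 0.50 × 0.20 = 10.0%;
- exponential: 0.25 × 0.091 = 2.3%; 0.50 × 0.091 = 4.6%.

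Even r = 60% with linear recovery gives 0.60 × 0.20 = 12%. All are below the 25% needed for a minor response, and a reduction cannot be progression. If a day-28 value later served as the lowest value, the rise to steady state would be at most 1/(1 - 0.10) - 1 = 11.1% for r = 50%, again below 25%. So the difference between the 4-week window and the 5-week recovery changes no category for r = 25-50%.

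**Step 4: which value the text points to.**
- The progression reference in Section 11.2 is a response value. Section 11.1 starts response assessment at Cycle 2, so a pre-dose Cycle 1 Day 1 IgM is not one.
- Sections 6 and 13.7.2 make a participant non-evaluable for response within 4 weeks of plasmapheresis. An IgM drawn 1-7 days afterwards lies well inside that period.
- Measurable IgM is an eligibility criterion met at screening (Section 3.1.4), and Section 11.1 speaks of the same measurable disease as present at baseline.
- Screening is the only pre-treatment IgM that every participant must have, since Cycle 1 Day 1 tests can be skipped.
- A trigger at 5,000 mg/dL normally rests on an IgM drawn before plasmapheresis.
- The calendar row also carries a mark at Screening, where no response can exist, so its mark at Cycle 1 Day 1 need not mean response scoring.

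**The case for a change.** The best case for a change is that no sentence closes the gap. A common programming default takes the last value before the first dose. When screening was more than 14 days earlier, Cycle 1 Day 1 tests are required, and that default would pick the lowered value. Two participants with the same disease could then be scored differently according to which tests were drawn. Section 13.7.2 does not help: it points to subsections 9.1.2 and 11.1.2, which do not appear under those numbers. With 50% removal the day before Cycle 1 Day 1 and a true 25% drug effect, IgM is 28-31% below its pre-plasmapheresis level, a minor response, yet about 33% above the lowered value (1.778 × 0.75 = 1.333).

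The arithmetic stands, and so does the omission. A participant already on plasmapheresis at screening might also have no undisturbed value in the trial record. What does not stand is that the plan itself selects the lowered value. Choosing it would mean ignoring the plan's own account of what plasmapheresis does to IgM, in a 30-participant study where individual IgM courses can be read by hand. The calendar also allows 3 days either way: with plasmapheresis the day before Cycle 1 Day 1, a Cycle 2 Day 1 two or more days early falls inside 4 weeks and is barred.

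Rebound after stopping a BTK inhibitor and the unstated reconfirmation interval are separate matters. The documents do not allow the first to be quantified.

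**Conclusion.** No change follows. The plan leaves one definition unwritten, and its other provisions lead analysts to the sensible choice: the screening value as baseline, with values soon after plasmapheresis set aside. On that reading the distortion at week 4 is a 2-10% false reduction, with no false progression and no false minor response. A false progression needs three things together: a reading the text does not call for, removal above about 24% (plasmapheresis one day before Cycle 1 Day 1) or 25-39% (seven days before), and little drug effect. These thresholds rest on assumed recovery curves over the stated 5 weeks; the documents give neither the share removed nor the number of participants affected, so no bias in PFS or loss of power can be claimed. The main outcome exposed is a secondary time-to-event estimate in a single-arm study, while ORR counts a response at any point on therapy.

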5.5 Criteria for Taking a Participant Off Protocol Therapy

Duration of therapy will depend on individual response, evidence of disease progression and tolerance. In the absence of treatment delays due to adverse event(s), treatment may continue for 18 cycles or until one of the following criteria applies:

- Disease progression.
- Intercurrent illness that prevents further administration of treatment.
- Unacceptable adverse event(s).
- Participant demonstrates an inability or unwillingness to comply with the oral medication regimen and/or documentation requirements.
- Participant decides to withdraw from the protocol therapy.

- General or specific changes in the participant's condition render the participant unacceptable for further treatment in the judgment of the treating investigator.

Participants will be removed from the protocol therapy when any of these criteria apply. The reason for removal from protocol therapy, and the date the participant was removed, must be documented in the case report form (CRF). Alternative care options will be discussed with the participant.

In the event of unusual or life-threatening complications, treating investigators must immediately notify the PI, [name] at [contact].

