11.3 Time-to-event definition

- Progression-Free Survival (PFS) is defined as the duration of time from start of treatment to time of objective disease progression (including initiation of new therapy or death).

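### Section 11.1 allows for IgM rebound after BTK-inhibitor withdrawal when response is judged, but the IgM-only progression rule in 11.2 has no matching exception

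*Combined protocol and SAP*

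**What the plan says.** **Entry.** Section 3.1.9 provides that participants progressing on a BTK inhibitor "may continue on therapy through screening, stopping at least 1 day prior to Cycle 1 Day 1".

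**Response.** In section 11.1, "Response will be assessed on Day 1 of each cycle starting with Cycle 2", with an exception for recent plasmapheresis. It then adds: "Participants discontinuing BTK inhibitors might not be evaluable for response due to IgM rebound until Cycle 4 Day 1". After that their response is classified by the definitions in 11.2. A closing note makes participants with objective progression or death before the end of cycle 1 evaluable as well.

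**Progression.** Section 11.2, headed Response Criteria, counts as progression a "greater than 25% increase in serum IgM level occurs with an absolute increase of at least 500 mg/dL from the lowest attained response value". The one safeguard for a rise in IgM alone is this: "Reconfirmation of the initial IgM increase is required when IgM is the sole criterion for progressive disease confirmation". BTK-inhibitor withdrawal is not mentioned.

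**Consequences.** Disease progression is a listed off-therapy criterion in 5.5, where "Participants will be removed from the protocol therapy when any of these criteria apply". PFS in 11.3 is the "duration of time from start of treatment to time of objective disease progression". ORR counts the best response while on therapy (11.2), and the Full Analysis Set is everyone who received at least one dose (13.5).

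**Analysis section.** Section 13.7.2 repeats the plasmapheresis exception but not the BTK-inhibitor one.

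**The concern.** Rebound raises IgM. The plan provides for it where it would hide a fall (response), but not explicitly where it would imitate a rise (progression). Both judgements rest on the same serum measurement in the same weeks.

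If a site takes 11.2 at face value, a participant whose IgM climbs because the BTK inhibitor was withdrawn, and whose repeat value agrees, has progressive disease. That participant comes off daratumumab, has a PFS event in the first weeks and, without an earlier response, can no longer become a responder but stays in the denominator. A different reading at analysis cannot restore the lost treatment. Two careful investigators could classify the same IgM curve differently.

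**Working it through.** **1. When the window closes.** Days are counted from the first dose, ignoring the ±3-day visit windows.

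- Cycle 2 Day 1: day 28.
- Cycle 3 Day 1 depends on how the 2-week start of consolidation (5.1) is counted. It is day 56 with no extra gap, 49 + 14 = 63 if counted from the Cycle 2 Day 22 infusion, or 56 + 14 = 70 if counted from the end of Cycle 2.
- Cycle 4 Day 1 is 28 days later: day 84, 91 or 98, that is weeks 12 to 14.
- Cycle 4 Day 15: day 98, 105 or 112, that is weeks 14 to 16.

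**2. Chances to meet the IgM rule before the window closes.** The study calendar (section 10) schedules IgM on Days 8, 15 and 22 of Cycle 1 (3 draws), all four treatment days of Cycle 2 (4) and Days 1 and 15 of Cycle 3 (2). That makes 3 + 4 + 2 = 9 post-baseline draws. Two response assessments, at Cycle 2 Day 1 and Cycle 3 Day 1, also fall before Cycle 4 Day 1. A rise seen at the first and repeated at the second satisfies 11.2 as written, reconfirmation included.

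**3. Size of rise needed.** The 25% and 500 mg/dL limits coincide at a reference IgM of 2,000 mg/dL (0.25 × 2,000 = 500). From an assumed reference of 3,000 the value must exceed 1.25 × 3,000 = 3,750 mg/dL. From 4,000 it must exceed 1.25 × 4,000 = 5,000 mg/dL. The documents do not say how often rebound is that large.

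**4. Effect on ORR.** One participant removed before responding, who would otherwise have responded, lowers the observed ORR by 1/30 = 3.3 points.

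**5. Effect on the PFS date.** The plan does not say whether progression is dated at the first rise or at reconfirmation. For a Cycle 2 Day 1 / Cycle 3 Day 1 call, the literal date is day 28 or day 56 to 70. If IgM-only progression cannot be called before Cycle 4 Day 1, the earliest date is day 84 to 98. That is 56 to 70 days later than first-rise dating, or 28 days later than reconfirmation dating. If the rise was only rebound and has subsided, there is no event.

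**6. Illustration on the decision rule (13.1: at least 18 of 30).** The plan's own figures reproduce. P(X ≥ 18) for X ~ Bin(30, 0.70) is 0.9155, against a stated 0.92. P(X ≥ 18) for X ~ Bin(30, 0.40) is 0.0212, or 0.0425 when doubled, against a stated two-sided 0.04.

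Now assume that k participants are removed for rebound and cannot respond, and that the other 30 − k respond at 70%:

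| k (assumed) | P(at least 18 responders) |
|---|---|
| 0 | 0.916 |
| 1 | 0.871 |
| 2 | 0.809 |
| 3 | 0.728 |

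Nothing in the documents supports one value of k over another, and k = 0 is possible.

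**The case against.** The strongest reply is that 11.1 already settles the matter. Participants not yet evaluable are later classified by the 11.2 definitions, progression is one of those, and section 1.1 treats response, stable disease and progression as one set of criteria. Purpose points the same way: rebound cannot create a false response, and a hidden early response costs nothing while treatment continues, so the clause does little unless it holds back early calls of progression. The reference in 11.2 is the lowest attained response value, which a participant not yet evaluable arguably does not have. The note on progression before the end of cycle 1 may only waive the one-cycle minimum, and it does not reach Cycles 2 and 3. Reconfirmation is required, the permissive wording leaves room for judgement, and endpoint source documents are collected centrally (Appendix B, 19.1).

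Much of this stands. The deferring reading is plausible, and a reader should not infer that the protocol instructs sites to call rebound progression. But the text is permissive, speaks of response only, and is not carried into 11.2, 5.5, 11.3 or 13.7.2. Reconfirmation is no barrier if rebound lasts as long as 11.1 allows. Central collection of documents does not say which reading applies.

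It is also fair that these participants may enter while progressing on the BTK inhibitor, so an early rise may be true progression. That is a real cost of any deferral.

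Two nearby gaps are separate clarifications and add no weight here. One is that IgM-only progression has no stated reconfirmation interval, while complete response needs "absence of IgM paraprotein by immunofixation by a measurement repeated at least 2 weeks later". The other is that the plasmapheresis exception is also silent on progression.

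**Conclusion.** The gap is real but modest. The plan recognises rebound until Cycle 4 Day 1 for response and leaves unsettled whether the same applies to IgM-only progression. On the literal reading the result is avoidable removal from therapy, an early PFS event and, without an earlier response, a non-responder in the Full Analysis Set. On the deferring reading there is no loss.

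The overall size cannot be fixed from the documents. The firm figure is 3.3 ORR points for each affected participant who would otherwise have responded. A reader might infer from the illustration that the trial's power falls to 0.81 or 0.73. The documents do not support that: the counts are assumed, and the comparison with 0.916 supposes that the affected participants would have responded at 70%. If they would have responded less often, the loss due to the wording is smaller. Nor does the gap inflate efficacy, since the error runs against the drug.

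This is a cheap improvement of minor to moderate severity, worth making mainly because removal at a site cannot be undone later.

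**What to change.** Add to 11.2, with a cross-reference in 5.5:

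- For participants who stopped a BTK inhibitor at study entry, an IgM rise alone before Cycle 4 Day 1 is not progressive disease and does not trigger removal under 5.5.
- IgM-only progression is called only if the threshold is met at Cycle 4 Day 1 or later and is reconfirmed. The IgM draw already scheduled for Cycle 4 Day 15 can serve.
- Such progression is dated at the first qualifying value at or after Cycle 4 Day 1. Dating it at an earlier rise would bring the rebound date back into PFS.
- Symptomatic, nodal, splenic, other extramedullary or transformation progression, new therapy and death count at any time, and the investigator may stop therapy on clinical grounds.
- Report how many participants the rule was applied to, with a sensitivity analysis applying 11.2 literally. The rule holds back IgM rises but not falls, so readers should see both results.

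**Cost.** This is protocol wording only; no visit or sample is added. A true IgM-only progression would be confirmed at Cycle 4 Day 15 instead of Cycle 3 Day 1. That is 28 + 14 = 42 days, about 6 weeks, later on every reading of the schedule, and the participant may stay on an ineffective drug unless stopped on clinical grounds. The rule also leaves the reference IgM value unchanged, so a rebound still above the threshold at Cycle 4 Day 1 and on the repeat would count as progression. If the sponsor prefers the literal reading, it should say so in 11.2 before IgM curves are classified.
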